**AcuWand Comfort Questionnaire (administered week 6).**

*Massachusetts General Hospital Acupuncture Sensation Scale (MASS)* consists of twelve predefined descriptors and one subjective component specified by the subjects in their own words to measure levels of *de qi* sensations.

*De qi* is a prerequisite term in Traditional Chinese Medicine (TCM) used to describe sensory stimulation. It has historically been thought to be an indicator of appropriate acupuncture or acupressure treatment and thus relates to therapeutic effectiveness.

Comfort level and ease of use of the AcuWand device will also be assessed.

## 5.0 REPORTING ADVERSE EVENTS

### 5.1 Definition

An adverse event (AE) is any condition which appears or worsens after a participant is enrolled in an investigational study. An AE does not necessarily have a causal relationship with the study agent.

### 5.2 Assessment of Relationship of AE to Treatment

The possibility that the adverse event is related to study treatment will be classified as one of the following: not related, unlikely, possible, probable, definite.

### 5.3 Study Specific Adverse Event Reporting Plan

All Serious Adverse Events that are deemed related, probably related or possibly related will be reported to the IRBMED within 7 days, as per UM IRBMED guidelines

All other non-serious, non-life-threatening adverse events will be reviewed by the PI and reported as per the following **Study Specific Adverse Event Reporting Plan**:

Reportable Events	Timing of Report to IRBMED
Unanticipated / unexpected problem involving risks to subjects or others	Serious - within 7 days  Non-Serious - with scheduled continuation review
Any physical, social, or psychological harm attributable to participation in this research study (e.g. an injury occurring during a study visit, bruising at the site of acupressure treatment)	Serious - within 7 days  Non-Serious - with scheduled continuation review
Death while on study	Within 7 days of notification
Loss of job or insurability due to breach or revelation of research records or participation.	Within 7 days of notification
Non-Reportable Events	
	

Hospitalizations and morbidity expected in population (e.g. surgery for removal of fibroid tumor)

Other serious or non-serious events deemed not related or unlikely related to the research

**Serious** = an event requiring hospitalization, permanent disability, incarceration, significant familial disruption (e.g. separation, divorce), job loss

**Non-Serious** = an event requiring some medical, psychological, psychiatric or similar attention to resolve.

**Scheduled continuation review** = renewal application.

#### 5.4 Follow-up of AEs

All AEs will be followed according to good medical practices, and documented as such.

#### 5.5 AE Reporting and Data Elements

All participants will be questioned regarding adverse events during the follow up phone call and final visit. All participants will be instructed to contact the study coordinator via phone call or email at any time during the study if they have a concern.

All adverse events that occur after the informed consent is signed will be recorded on the adverse event case report form (CRF) whether or not related to study intervention.

The following information will be collected for all adverse events:

- AE reported date
- AE Verbatim Term
- CTCAE Term (v 4.03)
- Event onset date and event ended date
- Severity grade
- Attribution to study treatment (relatedness)
- Whether or not the event was reported as a Serious Adverse Event (SAE)
- Action taken with the study intervention
- Outcome of the event
- Comments

#### 5.6 Severity of AEs

Severity will be graded according to NCI Common Terminology Criteria for Adverse Events (CTCAE) version 4.03. The CTCAE provides descriptive terminology and a grading scale for each adverse event listed. A copy of the CTCAE can be found at <http://ctep.cancer.gov>.

AEs will be assessed according to the CTCAE grade associated with the AE term. AEs that do not have a corresponding CTCAE term will be assessed according to their impact on the participant's ability to perform daily activities as follows:

Grade	Severity	Description
1	Mild	

• Asymptomatic or mild symptoms

• Clinical or diagnostic observations only

• Intervention not needed

2	Moderate	

• Minimal, local or non-invasive intervention indicated

• Limiting age-appropriate instrumental activities of daily living

3	Severe	
 
Medically significant but not immediately life-threatening
 
hospitalization or prolongation of hospitalization
 
Disabling
 
Limiting self-care activities of daily living
 

4	Life threatening	
 
Life threatening consequences
 
Urgent intervention needed
 

5	Death	
 
Death related to Adverse Event
 

## 6.0 CONCOMITANT MEDICATION, EXERCISE, DIET AND SMOKING

### 6.1 Limitations on Medication, Exercise, Diet and Smoking

Concomitant prescribed medications are allowed except as listed in Exclusion Criteria. Acute medication will be allowed, defined as taking a medication for < 10 days over the course of a month with the intent to discontinue that medication.

Similarly, participants will be asked (once consented) to maintain their customary exercise, dietary and smoking habits during the screening, intervention and follow-up phase of the study. Participants will be asked to refrain from starting or stopping any new lifestyle modifications for the entire duration of the study.

### 6.2 Documentation of Medication

All chronic medications (prescription or OTC used for at least 14 days continuously), dietary supplements and/or herbal preparations taken by the participant during the study period will be documented on a CRF with information including:

- Type of medication
- Medication dosage/schedule
- Purpose for taking the medication, supplements or herbs (if available)

## 7.0 OFF-STUDY CRITERIA

### 7.1 Study Termination

The study participant will be considered off-study when they complete the full study, as defined as completing the 24-week visit.

The Principal Investigator can decide to terminate a participant's participation in the study at any time. This decision could be based on factors such as unacceptable adverse events or for safety concerns. The reason for termination shall be documented in the case report form.

### 7.2 Premature Removal of a Participant

#### 7.2.1 Personal reason

A participant may withdraw from the study at any time; the reason will be documented in patient study records.

#### 7.2.2 Lost to follow-up

Three attempts must be made by telephone and letter to determine the circumstances for loss to follow-up, since such loss may be related to the study intervention.

### 7.2.3 Death

Participants who die while on study will be replaced by another participant.

### 7.2.4. Lost to follow-up after enrollment but withdrew before the baseline visit

Participants who withdraw between enrollment and the baseline visit can be replaced with a new participant

## 8.0 DATA MANAGEMENT

Study measures will be delivered electronically to participants using RedCAP. RedCAP is a generalized survey service supported by the University of Michigan Medical School permitting the creation and distribution of surveys, as well as data storage and analysis. RedCAP is user-friendly but can handle complex designs. For instance, simple surveys can be produced in minutes. Complex studies, involving randomization and embedded and longitudinal data, are also possible. RedCAP is also HIPAA compliant. RedCAP surveys will be accessed by the participant through an electronic device, via e-mail link forwarded from the study team, and are separate from the acupressure app. Those unable to effectively access and use these instruments will have a study team member administer these measures via phone, entered directly into RedCAP.

### Statistics Section.

The primary aim of this study is to investigate the differential effects of different modes of acupressure (relaxing vs. sham vs. no treatment) on fatigue as measured by the BFI in ovarian cancer survivors at week 6. The BFI, which measures the average degree of fatigue, gives a score that ranges between 0 and 10, with higher numbers indicating more fatigue. To investigate the difference in BFI between the three study arms, we shall use linear mixed-effects regression analysis with BFI as outcome, *week* as the within-subjects factor with four levels (0, 6, 12, 24) and *group* (relaxing acupressure, sham acupressure, no treatment) as the primary between-subjects factor. Of interest is the group-by-week interaction (to be included in the model), significance of which will indicate differences in extent of decrease between the arms. The covariate cancer stage at diagnosis and the interaction term group-by-stage will be added to models. Post-hoc sliced main effect of weeks within each study arm will be estimated. A *subject* random-effect will be used to account for the clustering effect within the four measurements on the same subject. Model diagnostics will be carried out to confirm the distributional assumptions and appropriate corrective actions (e.g. transformation) will be performed as needed. Models with more flexible covariance pattern (e.g. unstructured covariance, heterogeneity across groups) will be explored. An additional analysis with a spline version of weeks will be carried out which uses *week* as a continuous variable allowing one to estimate the rate of change in BFI.

A secondary analysis with BFI will also be carried out which investigates the difference in proportion of fatigued subjects ( $BFI \geq 4$ ) across the three study arms. The analytical framework will be that of a mixed-effects logistic regression model with presence of fatigue ( $BFI \geq 4$  yes/no) being the dichotomous outcome. Apart from group, week, and group-by-week interaction as primary covariates, the model will also be adjusted for baseline status of severity. Remaining covariates in the model are identical to those in the continuous BFI model. The clustering effect due to subject will be accounted for using a generalized estimating equations approach under a generalized linear mixed models framework.

Secondary Aims. Analogous linear mixed-effects regression analyses as described in the primary outcome analysis will be employed to investigate our secondary outcomes at week 6 the **Secondary Aim “B”**, FACT-O, of which we will use two of the Functional Assessment of Cancer Therapy general subscales (PWB and FWB) plus the FACT-O subscale summed to represent our quality of life outcome; and **Secondary Aim “C”**; PSQI, which has scores for seven components, namely sleep quality; sleep latency; sleep duration; habitual sleep efficiency; sleep disturbances; use of sleep-promoting medication; and daytime dysfunction, all derived from the original PSQI. The component scores are summed to obtain a total score, the outcome for the proposed study.

Since PSQI score greater than 5 is considered an indicator of poor sleep quality, we shall also carry out a logistic regression analysis with a dichotomous outcome indicating whether  $PSQI > 5$  is satisfied or not. This will compare the proportions (longitudinally) of subjects with poor sleep quality across the study arms. The analytical framework will be very similar to that for testing equality of proportions of subjects that are fatigued.

**Exploratory Aims.** Analogous linear mixed-effects regression analyses as described in the primary outcome analysis will be employed to investigate our exploratory outcomes (all administered on weeks 0, 6, 12, and 24) the summation of the PROMIS Short Form questions covering: anxiety, depression, pain interference, sleep disturbance, cognitive function, and sexual function and satisfaction profile.

To investigate the duration of effect of self-administered relaxing acupressure as compared to self-administered sham acupressure or no treatment during the 18 weeks following the end of acupressure treatment (carry-over phase) on persistent fatigue, quality of life, sleep quality, and symptoms commonly associated with persistent fatigue (sleep disturbance, pain, cognitive function, mood, and female sexual function) we will break up the observation period into two phases. In the first phase BFI and other study measures will be obtained by averaging week 0-week 6 measures and will indicate the status until end of the acupressure treatment (treatment-phase). The second phase comprises of week 7-week 24 and indicates the washout phase (washout). To investigate the difference in BFI and other study measures between the three study arms, we shall use mixed- effects regression analysis with average BFI and other study measures in the two phases as outcome, phase as the within-subjects factor and group (RA, SA, standard of care) as the primary between-subjects factor. We shall carry out an analysis with the phase variables as treatment-phase and washout as the levels. The purpose of investigating the model will compare the differences between the treatment and washout period across groups (phase-group interaction).

**Handling Missing Data.** The *linear mixed-effects* framework is an intent-to-treat framework in the sense that it uses all available data at all time-points. So if there are missing outcome values in any phase due to participant dropout, the usual analysis will still be valid. If the proportion of dropouts is substantial (20% or more) in either arm, then we shall also perform a weighted analysis with weights equal to the inverse of the probability of dropout. On the other hand, missing covariate values for the subject-level information will be imputed using multiple imputation methods. All missing values will be imputed using the chained equation method. The advantage of using this technique is its flexibility in allowing different types of variables (categorical and continuous) to be imputed together without requiring any multivariate joint distributional assumption. In this method, the missing values are sequentially updated using bootstrap or Markov Chain Monte Carlo based on multiple regression models with other variables as covariates. This procedure will be carried out for a number of repetitions or cycles, thereby constructing an ‘imputed’ dataset. Ten such ‘imputed’ datasets will be used for the final analysis, a number which is considered adequate for most applications. Finally, we shall combine the results from the ten regressions with the imputed data using Rubin’s formula.

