**Screening.** All potential participants will be screened over the phone using a basic questionnaire to confirm their eligibility. Specifically, an abbreviated form of the *Patient Health Questionnaire (PHQ-2)* will be used to detect untreated depression, and the *Brief Fatigue Index (below; BFI)* will be used to determine fatigue. These measures will be collected before consent and enrollment in to the study and will therefore be kept to the absolute minimum to determine eligibility.

Rescreening. Participants may be rescreened at 6 weeks after initial screening if they failed their initial screening based on: stable chronic medications and no new planned interventions for their fatigue or cancer.

**Fatigue Measure (administered at screening and weeks 0, 6, 12, 24).** *Brief Fatigue Inventory (BFI)* will be used to assess the severity and impact of fatigue on daily functioning. The BFI is a scale validated in cancer patients with an alpha coefficient exceeding 0.95, which correlates well with other fatigue measures. The BFI assesses severity and impact of fatigue in cancer patients over the past 24 hours. The instrument consists of 9 items, each measuring fatigue on a 0-10 scale, and is calculated from the mean of completed items. Scores of  $\geq 4$  indicate clinically- relevant fatigue. A three-point change or a drop below 4 is considered a clinically meaningful change.

**Sleep Quality (administered weeks 0, 6, 12, 24).** *Pittsburgh Sleep Quality Index (PSQI)* is widely used 19-item questionnaire evaluates sleep disturbance over the past month. It yields a total score and 7 component scores: sleep quality; sleep latency; sleep duration; habitual sleep efficiency; sleep disturbances; use of sleep-promoting medication; and daytime dysfunction. In women with breast cancer, Cronbach's alpha for the global PSQI is 0.80. A score  $>7$  in breast cancer patients and thus likely in ovarian cancer patients suggests poor sleep quality. The scale has adequate psychometrics. The primary outcome will be the total PSQI score at baseline and week 6, although we will conduct exploratory analyses on the PSQI subscales.

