## 9.0 STATISTICAL METHODS

**Power Analysis.** Our power analysis is based on our primary aim to, “Examine the effect of 6 weeks of daily self-administered relaxing acupressure compared to self-administered sham acupressure or no treatment on persistent fatigue as measured with The Brief Fatigue Inventory.” Although we will run a larger model for the analysis, in the power calculation we focus on the specific components of the model in which we are interested. Towards that end, we compute the power via simulation using a mixed effects model with a between-subject factor group (3 levels), a within-subject factor week (0, 6, 12, and 24), group-by-time interaction and a random subject effect. The mean BFI at baseline is assumed to be 5.5, whereas values at end of treatment were assumed to be 4.5, 3.5, and 2, respectively for no treatment, sham acupressure and relaxing acupressure arms. The between-subject variance is assumed to be 4 at all time-points whereas the variance of the random subject component is taken to be 4 also (yielding an intra-class correlation of 0.5). These assumed values are estimates based on our pilot data. For this configuration, the power for detecting a significant week-by-group interaction is greater than 95% with a sample size of 50 evaluable participants per treatment arm (we anticipate a ~13 % drop out with the goal of 150 completers for a total sample size of 171) and a 5% level of significance. Such a model is able to detect a post-hoc difference between the relaxing acupressure and each of the other two arms with more than 90% power at a reduced 0.01 level of significance in order to protect against Type I error probability inflation. In the second phase after the treatment period, it is anticipated that both the no-treatment and the sham acupressure arms will experience a bounce

back close to the baseline level, while the relaxing acupressure arm will maintain its end-of-treatment average. Thus, the differences will be more pronounced than those in the active treatment phase, and we will be well

powered to detect the effect size.

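### The primary BFI model does not condition on baseline BFI, so the week-6 relaxing versus sham contrast is unbiased but less precise than the collected data allow

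*Combined protocol and SAP*

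**What the plan says.** The Statistics Section sets up a linear mixed model for BFI with week "as the within-subjects factor with four levels (0, 6, 12, 24) and" study group as the between-subjects factor. The effect of interest is "the group-by-week interaction (to be included in the model), significance of which will indicate differences in extent of decrease between the arms". On covariates it says "The covariate cancer stage at diagnosis and the interaction term group-by-stage will be added to models". Correlation is handled by a subject term: a "random-effect will be used to account for the clustering effect within the four measurements on the same subject". No common week-0 mean is imposed. Neither the flexible-covariance models nor the spline version adds baseline BFI.

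For the secondary logistic model of BFI 4 or more, the same section says "the model will also be adjusted for baseline status of severity". So baseline adjustment is used in the plan, but not in the primary model.

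Section 4.1 (Fatigue Measure) has the BFI "administered at screening and weeks 0, 6, 12, 24", and its Screening paragraph says the screening score is collected before consent and enrolment.

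**The concern.** Randomisation makes the arms equal in expectation on anything measured before allocation. A model that estimates a separate week-0 mean per arm and then subtracts it carries the sampling noise of those means into the treatment contrast. Conditioning on baseline removes part of that noise.

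The listed covariates do not do this job. Stage and group-by-stage are constant over time, so with complete data they leave a within-woman change contrast unchanged.

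Relaxing versus sham matters most here. Section 4.0 says the sham arm is there to isolate the specific effect of relaxing acupressure, and section 9.0 assumes a smaller difference for this comparison (3.5 − 2 = 1.5) than for relaxing versus no treatment (4.5 − 2 = 2.5).

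**Working it through.** **Inputs (section 9.0).** 50 evaluable women per arm; baseline mean 5.5 in all arms; week-6 means 4.5 (no treatment), 3.5 (sham) and 2 (relaxing); pairwise level 0.01, taken as two-sided because the plan does not say. On variance: "The between-subject variance is assumed to be 4 at all time-points" and the "variance of the random subject component is taken to be 4 also (yielding an intra-class correlation of 0.5". This can be read as 4 + 4 = 8 in total, or as 4 in total with half between women. Both are carried below.

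**The plan's own figures first.** Powers are from the noncentral F and t distributions.
- Interaction, weeks 0 and 6 only, residual variance 4. The mean changes are −1, −2 and −3.5, and their squared deviations sum to 3.167. The noncentrality is 50 × 3.167 / 8 = 19.8 on 2 and 147 df, giving 98%. The stated power above 95% is reproduced.
- Relaxing versus no treatment (2.5) at 0.01, total variance 8: 96%. The stated power above 90% is reproduced.
- Relaxing versus sham (1.5) at 0.01, as a week 0 to 6 change contrast: 51% (total variance 8) or 87% (total variance 4). The 87% lies about one Monte Carlo standard error below 90%, since √(0.9 × 0.1 / 100) is 3 points with the plan's 100 simulations. The plan does not say which contrast was simulated.

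**Per-woman variance of the two estimators.** Let s0 and s6 be the SDs at weeks 0 and 6, and ρ their correlation.
- Change score: s0² + s6² − 2ρ·s0·s6
- Conditional on baseline: s6²(1 − ρ²)
- With s0 = s6 the ratio is (1 + ρ)/2, so the saving is (1 − ρ)/2.

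**Equal variances.** The savings are 35%, 25% and 15% at ρ = 0.3, 0.5 and 0.7. At total variance 8 and ρ = 0.5, the change variance is 8 and the conditional variance is 6. The between-arm contrast has variance 2 × 8 / 50 = 0.32 against 2 × 6 / 50 = 0.24. An exact generalised least squares calculation for three arms, four weeks and a random intercept, comparing free with common week-0 means, gives the same 0.32 and 0.24.

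**Power for a difference of 1.5 (98 df, ρ = 0.5, equal variances).**

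| Total variance | Contrast variance | Noncentrality | Power at 0.01 | Power at 0.05 |
|---|---|---|---|---|
| 8 | 0.32 → 0.24 | 2.65 → 3.06 | 51% → 67% | 75% → 86% |
| 4 | 0.16 → 0.12 | 3.75 → 4.33 | 87% → 95% | 96% → 99% |

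**Unequal variances.** Entry requires BFI of at least 4, which may narrow the week-0 spread. The documents give no week-0 SD, so the ratio k = s0/s6 is an assumption. At ρ = 0.5, in units of s6²:
- k = 0.85: change 0.7225 + 1 − 0.85 = 0.8725; conditional 0.75; saving 14%.
- k = 0.70: change 0.49 + 1 − 0.70 = 0.79; conditional 0.75; saving 5%.

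If the floor holds fully at week 0, scores between 4 and 10 with mean 5.5 have variance of at most (5.5 − 4)(10 − 5.5) = 6.75. A week-0 variance of 8 is then impossible.

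**The case against.** The strongest reply is that the planned analysis is a standard repeated-measures model. It is unbiased, and its prespecified interaction test has ample power on the plan's own inputs, as does relaxing versus no treatment. That stands: the gain matters mainly for one pairwise contrast.

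The size is also uncertain. A reader might infer that a quarter of the variance is certainly lost, but the documents give neither a week 0 to 6 correlation observed in this population nor a week-0 SD. The only observed SDs of change, in Table 3, run from 1.5 to 2.0. With the pooled 1.7 of section 9.2 and a difference of 1.5, the change contrast already has 96% power at 0.01, and a 25% saving takes it to 99%. At the difference actually tabulated (1.9621 − 1.2988 = 0.663), the same saving with 50 per arm moves power at 0.05 from 49% to 61%, so the benefit does not vanish.

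The Statistics Section names an interaction and within-arm week effects, but no between-arm contrast at week 6. If the unadjusted week-6 means were compared instead, the saving would be ρ²: 9%, 25% and 49% at ρ = 0.3, 0.5 and 0.7. The two readings agree at 0.5.

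A reader might also think that forcing a common week-0 mean is a cost-free remedy. The documents do not support that. Section 3.0 puts random assignment and shipment in weeks −1 to 0, and section 3.3 leaves the no-treatment arm unblinded, so a week-0 survey could be answered with the allocation known. Nor is the common-mean model strictly equivalent to the covariate model under a random-intercept covariance or with missing data.

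**Conclusion.** The point holds as one of efficiency. The primary model does not condition on a baseline the trial already collects, and the change contrast for relaxing versus sham at week 6 is less precise for it. The saving is 25% at ρ = 0.5 with equal variances, 15% to 35% for ρ from 0.7 to 0.3, and about 14% or 5% at ρ = 0.5 if the week-0 SD is 0.85 or 0.70 of the week-6 SD. The power gains at 0.01 (51% to 67%, or 87% to 95%) assume 50 per arm, a difference of 1.5, ρ = 0.5 and equal variances, and depend on which reading of the section 9.0 variances is meant.

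Two stronger readings should be resisted. The planned model is not biased and does not inflate type I error. And the gap between these figures and the stated pairwise power above 90% is a separate matter: it turns on the ambiguous variances and the unstated contrast, and failure to adjust for baseline does not explain it.

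**What to change.** In the Statistics Section, model BFI at weeks 6, 12 and 24 with group, week, group-by-week and baseline BFI-by-week as a covariate, preferably with an unstructured covariance. Name relaxing minus sham and relaxing minus no treatment at week 6 as the reported contrasts. Because the baseline slope is estimated from the data, this form is, in large samples with 1:1:1 allocation, no less precise than the change contrast whatever the SD ratio.

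State which baseline is used. Week-0 BFI qualifies only if it was completed before the woman knew her allocation; otherwise use the pre-randomisation screening BFI. The screening score may also be added as a second covariate, with a smaller gain expected because its range is restricted.

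Section 9.2 and Tables 3 and 4 report week-6 results without naming their source. If they come from this trial, the baseline-adjusted model should be labelled a supplementary analysis, since it would be chosen after a true versus sham p-value of 0.078 had been seen.

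The cost is a few sentences in the analysis plan, with no new data and no more participants. The secondary and exploratory outcomes use analogous models, so the same wording can serve them with their own week-0 scores, under the same timing condition; they have no screening score to fall back on.

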## 2.0 SPECIFIC AIMS

To investigate our hypothesis, we will randomize fatigued ovarian cancer survivors into 6 weeks of daily: 1. Relaxing self-acupressure (n=57); 2. Sham self-acupressure (n=57); or 3. No treatment (n=57) followed by 18 weeks of no acupressure and investigate the following aims:

1. Examine the effect of 6 weeks of daily self-administered relaxing acupressure compared to self-administered sham acupressure or no treatment on:

- A. Persistent fatigue (**Primary aim**) -- measured with The Brief Fatigue Inventory;
- B. Quality of life (**Secondary aim**) -- using the Functional Assessment of Chronic Illness Therapy Measurement System, specifically the ovarian cancer specific instrument;
- C. Sleep Quality (**Secondary aim**) -- using the Pittsburgh Sleep Quality Index;
- D. Symptoms commonly associated with persistent fatigue (**Exploratory aim**) (sleep disturbance, pain, cognitive function, mood, and female sexual function) -- using Patient Reported Outcomes Measurement Information System.

**2 (Exploratory aim).** To investigate the duration of effect self-administered relaxing acupressure as compared to self-administered sham acupressure or no treatment during the 18 weeks following the end of acupressure treatment (carry-over phase) on persistent fatigue, quality of life, sleep quality, and symptoms commonly associated with persistent fatigue (sleep disturbance, pain, cognitive function, mood, and female sexual function) using the measurement tools described for the primary aim.

Both acupressure treatments will be delivered via the MeTime Acupressure app in association with the AcuWand.

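### The primary aim is fatigue at week 6, but the effect the plan tests is the arm-by-week interaction over all four weeks, and no week-6 comparison between arms is named

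*Combined protocol and SAP*

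**What the plan says.** The Statistics Section places the primary aim at one time point: the effect of the three arms "on fatigue as measured by the BFI in ovarian cancer survivors at week 6". The model is a linear mixed model with week as a four-level factor (0, 6, 12, 24), arm, their interaction and a random subject effect. The effect it singles out is: "Of interest is the group-by-week interaction (to be included in the model), significance of which will indicate differences in extent of decrease". The one follow-up it names is "Post-hoc sliced main effect of weeks within each study arm will be estimated". The Secondary Aims paragraph carries this over to FACT-O and PSQI: "Analogous linear mixed-effects regression analyses as described in the primary outcome analysis will be employed to investigate our secondary outcomes at week 6".

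Section 2.0 makes the period after treatment exploratory. Aim 2 there reads: "To investigate the duration of effect self-administered relaxing acupressure as compared to self-administered sham acupressure".

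Section 9.0 (Power Analysis) powers the same four-week interaction at 5% and adds that the model can "detect a post-hoc difference between the relaxing acupressure and each of the other two arms with more than 90% power at a reduced 0.01". It does not say at which week. Section 9.2 and Tables 3 and 4 report unadjusted pairwise comparisons of change from baseline to week 6, judged at 0.05.

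**The concern.** A 3-by-4 interaction asks whether the arms' profiles differ anywhere over 24 weeks. The primary aim asks whether they differ at week 6. The within-arm week effects do not bridge the two, because they compare weeks and not arms. Weeks 12 and 24 belong to an exploratory aim, yet they contribute to the primary test, and Section 9.0 expects arm differences to be larger there than during treatment.

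Read literally, a significant interaction could be reported as success on the primary aim when the arms do not differ at week 6. The 0.01 comparisons prevent this only if they are taken at week 6. On that reading a second matter arises: whether the power quoted for relaxing versus sham, the comparison that isolates the specific effect of the acupoints, is right for that week.

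**Working it through.** **Inputs (Section 9.0).** There are 50 evaluable per arm. Baseline mean is 5.5, and "values at end of treatment were assumed to be 4.5, 3.5, and 2, respectively for no treatment, sham acupressure and relaxing acupressure arms". The week-6 differences are therefore 3.5 − 2 = 1.5 (relaxing vs sham) and 4.5 − 2 = 2.5 (relaxing vs no treatment). On variances, one component is 4 and "the variance of the random subject component is taken to be 4 also (yielding an intra-class correlation of 0.5". This can be read two ways:

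- residual 4 plus subject 4, the more literal reading;
- total 4, so residual 2 plus subject 2.

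Both give an intra-class correlation of 0.5. Results are for residual variance s² = 4, with s² = 2 in brackets. Tests are taken as two-sided.

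**Step 1: reproduce the plan's figure.** Numerator df = (3−1)(4−1) = 6; denominator df = 3 × 49 × 3 = 441; noncentrality λ = 50 × (sum of squared interaction effects) / s². The means after week 6 are described but not given as numbers. If sham and no treatment return to 5.5 and relaxing stays at 2, the sum is 5.875, λ = 50 × 5.875/4 = 73.4 and power is above 99%. If all arms hold their week-6 values, the sum is 2.375, λ = 29.7 and power is 99%. The stated figure of more than 95% reproduces.

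**Step 2: the same test with no week-6 difference.** Assumed means over the four weeks: relaxing 5.5, 4, 4, 4; the other two arms 5.5, 4, 4+g, 4+g. The sum of squared interaction effects is (2/3)g², so λ = 50 × (2/3)g²/s².

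| Gap g at weeks 12 and 24 | λ | Interaction significant at 5% |
|---|---|---|
| 0.5 | 2.1 (4.2) | 15% (28%) |
| 0.75 | 4.7 (9.4) | 31% (60%) |
| 1.0 | 8.3 (16.7) | 54% (88%) |
| 1.5 | 18.8 (37.5) | 92% (>99%) |

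**Step 3: the 0.01 contrasts taken at week 6, same scenarios.** In 20,000-run simulations at gaps of 0.75, 1.0 and 1.5, a false relaxing-vs-sham claim occurs in about 1% of trials. A false claim against either arm occurs in 1.7–2.0% if the interaction must also be significant, and in 1.8–2.1% if not.

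**Step 4: week-6 power at 0.01 on the plan's means.** The SD of change is √(2s²) = 2.83 (2.00). At an intra-class correlation of 0.5 this is also the SD of the week-6 score itself. SE = SD × √(2/50) = 0.566 (0.400).

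- Relaxing vs sham: 1.5/SE = 2.65 (3.75); power 51–53% (87–88%), the range covering t with 98 to 441 df and the normal approximation.
- Relaxing vs no treatment: 2.5/SE = 4.42 (6.25); power 96–97% (>99%).
- Relaxing vs sham adjusted for baseline BFI, SD = √(2s² × 0.75): 67–69% (95–96%).

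**Step 5: could simulation error explain the stated figure?** Section 9.0 reports 100 simulations, so the standard error near 90% is √(0.9 × 0.1/100) = 3 points. More than 90 significant runs in 100 has probability 15–23% if true power is 87–88%, and practically none if it is 53%.

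**Step 6: reported results.** From Table 3 the pooled SD is 1.728 on 134 df. True vs sham: −0.66, SE 0.373, 99% CI −1.64 to 0.31, p = 0.078. True vs usual care: −1.53, SE 0.362, 99% CI −2.48 to −0.58, p < 0.001.

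**The case against.** The strongest reply is that Section 9.0 already supplies the contrast. It starts from the primary aim and gives numerical means only up to the end of treatment. It then states the 0.01 comparisons and only afterwards turns to the second phase. Table 4 also uses change to week 6. On this reading little more than the words *at week 6* is missing. That reading is plausible and, if adopted, largely closes the first gap. But the plan does not state it, the comparisons stand only in the power section, and Table 4 uses a different method and level (unadjusted, 0.05).

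Second, the two complaints rest on opposite readings. If the 0.01 comparisons span all four weeks, the power claim is not shown to be wrong: a 3-df relaxing-vs-sham interaction at 0.01 with s² = 4 has more than 99% power if sham returns to 5.0 or 5.5, and 97% if to 4.5. This is correct, so the two complaints should not be added together. Each reading still leaves something to correct: either no week-6 contrast is specified, or its power is overstated. The exception is the week-6 reading with s² = 2, where the shortfall is 2–3 points and within simulation error.

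Third, the late-only scenario is an assumption. The plan expects differences at week 6, and Section 4.0 describes improvement over six weeks followed by a plateau. The scenario shows what the test permits, not what is likely.

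Fourth, demoting the interaction may go further than needed. Step 3 shows that keeping it as a first gate changes little, so that choice can be left to the sponsor.

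**Conclusion.** The concern holds, and the plan should be corrected. The test named for the primary aim does not answer the week-6 question. With no week-6 difference it is significant in 15–92% of trials at residual variance 4, and in 28% to more than 99% at variance 2, for assumed later gaps of 0.5 to 1.5 points.

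If the 0.01 comparisons are taken at week 6, false claims in those scenarios fall to about 1% for relaxing vs sham and about 2% for either comparison. Relaxing-vs-sham power is then 51–53% or 87–88%, depending on the variance reading, against a stated figure above 90%. Relaxing vs no treatment is adequately powered on both readings.

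These figures rest on 50 evaluable per arm, two-sided tests, an intra-class correlation of 0.5 and the plan's week-6 means. On the Table 3 summaries the reported verdicts would not change at 0.01. That is an unadjusted analysis of 137 participants, so it does not settle what the planned mixed model would give.

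**What to change.** - **Statistics Section, primary analysis:** state that the primary aim is decided by the between-arm contrasts of change from week 0 to week 6 from the planned mixed model, relaxing vs sham and relaxing vs no treatment, each at the 0.01 already stated. Report the four-week interaction at 5% and the within-arm week effects as supportive, or keep the interaction as a first gate and say so.
- **Secondary Aims paragraph:** name the same week-6 contrasts for FACT-O and PSQI.
- **Section 9.0:** add the week to the 0.01 comparisons, state which variance reading applies, and restate relaxing-vs-sham power as about 51–53% (residual variance 4) or 87–88% (residual variance 2). Adjusting for baseline BFI is optional, uses data already collected, and gives 67–69% or 95–96%.
- **Disclosure:** because Section 9.2 and Tables 3 and 4 already report week-6 results, label the change as made after them and report the four-week interaction test beside the new contrasts.

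The cost is wording in three places and two contrast statements, with no new data. The omnibus test no longer carries the primary claim, the stated power becomes less favourable, and the late timing of the change has to be acknowledged.
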